### 3.2 Number of Sites

The study will be conducted at approximately 15 to 20 sites in the United States (US), Europe, and Australia.

Sites that do not enroll subjects into an open cohort within 6 months of site initiation may be closed.

### 3.3 Number of Subjects

Participants in this clinical investigation shall be referred to as “subjects”.

Approximately **54** subjects will **be enrolled** in this study **in order to ensure approximately 30 evaluable subjects in Period 1 and up to 15 evaluable subjects in Period 2 are treated with blinatumomab. It is expected that approximately 20% of subjects will discontinue the study prematurely (ie, due to adverse event, subject request, requirement for alternative therapy) during the cIV run-in period**

(Cycle 1/Period 1) or prior to receiving sufficient SC dosing (Cycle 1/Period 2 weeks 1 to 3) and will need to be replaced per [Section 3.4](#). Refer to [Section 10.2](#) for sample size considerations.

### 3.4 Replacement of Subjects

Subjects enrolled may be replaced if they are not evaluable for DLT during the DLT observation period as described in [Section 6.2.1.2.2](#).

#### 3.4.1 Replacement Rules in Cycle 1/Period 1

Subjects may be replaced for any of the following reasons:

- failing to complete all 3 cIV dosing levels during cIV run-in (weeks 1 to 3)
- failure to receive **all doses (q48h, q72h, q96h, or q7d dosing)**, at least 4 of the 5 doses (q24h dosing), or at least 8 of 9 doses (q12h dosing) during the SC treatment period (week 4)
- withdrawal from study for DLT without having had PK assessments (subjects who withdraw due to DLT are evaluable from a safety standpoint, but may not be evaluable from a PK standpoint if they have not completed their PK blood draws)
- subjects may be replaced if they miss the PK assessment time point and are unable to resume dosing and PK assessments
  - Note: Subjects who miss a dose before any PK assessments will default to the day of the missed dose. PK assessments will be performed per [Table 4](#) following the subject's resumed dose of investigational product (IP). For example, if a subject misses the dose on study day 2, the restart treatment day will be considered as study day 2 and all applicable assessments will be done per Schedule of Assessments (refer to [Table 3](#) and [Table 4](#) for further details)
- for all subjects who miss PK samples, the PK scientist will evaluate the PK results for this subject, and determine if the subject needs to be replaced, or if the PK results are sufficient for analysis. The DLRT will be informed of this decision to replace or not replace individual subjects at the time of the DLRT meeting.
  - subjects who do not complete PK assessments may continue on study, even if replaced

#### 3.4.2 Replacement Rules in Cycle 1/Period 2

Subjects may be replaced for any of the following reasons (except subjects removed for DLT that will never be replaced):

- failure to receive **at least 85% of the first 8 planned doses during the SC treatment period as outlined in [Table 6](#) (this would include 5 doses of step dose run-in and 3 doses at MTD)**

Approved

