#### 6.2.1.2.2 Dose Limiting Toxicity Rules

##### Cycle 1/Period 1

The DLT evaluation period includes the entire **week 4 (7 days) which is the week that blinatumomab is administered** SC during Cycle 1/Period 1 of the study. To be evaluable for a DLT, subjects must have experienced a DLT within the DLT evaluation period. In addition, if the investigator and/or sponsor removes the subject from the study due to a treatment-related toxicity during the DLT evaluation period, regardless of the grade of toxicity, this will be considered a DLT. If a subject does not experience a DLT during the DLT evaluation period and does not receive **all doses (q48h, q72h, q96h, or q7d dosing)**, at least 4 of the 5 doses (q24h dosing), or at least 8 of 9 doses (q12h dosing) of **SC** blinatumomab during Cycle 1/Period 1 of the study, the subject will not be considered DLT-evaluable and will be replaced as described in [Section 3.4.1](#).

If  $\leq 1$  of the 6 evaluable subjects in a dose SC cohort experience a DLT during the SC administration, then the dose will be determined to be tolerable and the next dose-cohort level will be initiated in a new dose-cohort of subjects after review by the DLRT.

If  $\geq 2$  subjects of the 6 evaluable subjects in a SC dose cohort experience a DLT during SC administration then dosing will stop for individual subjects who experience a DLT, a DLRT meeting will be conducted, and further steps will be determined.

Additionally, the DLRT will meet:

- once dose-cohort 1 has completed subcutaneous dosing
- once dose-cohorts 2 and 3 have completed subcutaneous dosing
- once any additional cohorts complete dosing if additional dose-cohorts are tested to determine the MTD in Cycle 1/Period 1

## Cycle 1/Period 2

For subjects who receive optional Cycle 2 after Cycle 1/Period 2 (SC dosing period), the DLT evaluation period includes the entire duration of SC administration **in Cycle 1** and 16 days following the last SC dose (56 days in total) or until the start of optional Cycle 2, whichever is longer, up to 30 days after the last SC dose **of Cycle 1**.

For subjects who do not receive optional Cycle 2, the DLT evaluation period includes the entire duration of SC administration and 30 days following the last SC dose (70 days in total).

Continuous monitoring for early termination of the trial will be performed (refer to [Section 10.2](#)).

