##### 10.1.2.3 DLT Analysis Set

All subjects who are DLT-evaluable are included in this analysis set as defined in [Section 6.2.1.2.2](#).

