If the outcome of the underlying disease is worse than that which would normally be expected for the subject, or if the investigator believes there is a causal relationship between the IP(s)/study treatment protocol required therapies and disease worsening, this must be reported as an adverse event or a serious adverse event. [Table 3](#) outlines the expected Disease-Related Events by System Organ Class (SOC).

Table 3. Disease-related Adverse Events by System Organ Class

System Organ Class (SOC)	Preferred Terms
Blood and lymphatic system disorders	Lymphadenopathy
General disorders and administration site conditions	Disease progression Fatigue
Investigations	Weight decreased
Skin and subcutaneous tissue disorder	Night sweats

Disease Related Events that would qualify as an Adverse Event or Serious Adverse Event:

- An event based on the underlying disease that is worse than expected as assessed by the investigator for the subject's condition or if the investigator believes there is a causal relationship between the investigational product(s)/study treatment/protocol-required therapies and disease worsening, this must be reported as an Adverse Event or Serious Adverse Event.

DLT Evaluable

Period 1:

To be evaluable for DLT, subjects must meet one of the following criteria:

- Cohort I and II: received treatment for or at least 8 of the 9 doses or experienced a DLT at any time while receiving blinatumomab.
- Cohort III: treated at least 4 of the 5 doses or experienced a DLT at any time while receiving the target dose of blinatumomab.

If a subject does not experience a DLT during the DLT evaluation period and does not receive all doses (q48h, q72h, q96h, or q7d dosing), at least 4 of the 5 doses (q24h dosing) or at least 8 of the 9 doses (q12h dosing) of subcutaneous Blinatumomab and taken off study for reasons other than toxicity the subject will not be considered DLT-evaluable and will be replaced as described in Protocol Section 3.4.1.

Period 2:

To be evaluable for DLT, subjects must meet one of the following criteria:

- If only cycle 1 is given : experienced a DLT during the entire duration of the SC administrations and 30 days after the last SC dose or treated with blinatumomab targeted dose for 5 days.

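### Period 2 DLT evaluability for subjects given Cycle 1 only is defined differently in the protocol and the SAP, and neither rule requires observation to the end of the DLT window

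*Protocol*

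**What the plan says.** **Protocol.** Section 10.1.2.3 defines the DLT set by reference: "All subjects who are DLT-evaluable are included in this analysis set as defined in" Section 6.2.1.2.2. The lead-in to Section 3.4 points to the same place: "Subjects enrolled may be replaced if they are not evaluable for DLT during the DLT observation period as described in" that section. For Period 1, Section 6.2.1.2.2 sets minimum dose counts and says that below them "the subject will not be considered DLT-evaluable and will be replaced as described in" Section 3.4.1. For Period 2 it gives only the window. Without Cycle 2, "the DLT evaluation period includes the entire duration of SC administration and 30 days following the last SC dose (70 days in total". The one Period 2 exposure test in the protocol is in Section 3.4.2. A subject may be replaced for not receiving "at least 85% of the first 8 planned doses during the SC treatment period", with the explanation that "this would include 5 doses of step dose run-in and 3 doses at MTD".

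**SAP.** Section 6 (DLT Evaluable, Period 2) makes a Cycle 1-only subject evaluable after a DLT during SC administration and "30 days after the last SC dose or treated with blinatumomab targeted dose for 5 days". Section 7.3 sends the DLT set to Section 8.1.1.2, whose Period 2 text again gives only the window. Section 11 states that nothing departs from the protocol-specified analyses.

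**The concern.** A DLT proportion needs one rule for who counts as a subject without an event. Here there are two. They are written in different units (a share of 8 planned doses, against days at the target dose), and they can classify the same subject differently.

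Both rules are also met early in a window of about 70 days. A subject who meets either one and then leaves observation without a DLT can enter the denominator as DLT-free for time that nobody observed. DLTs are part of the primary endpoint, and the Period 2 stopping boundaries count them. If such subjects are counted against Table 10, the observed rate is pulled down and the boundary is harder to reach.

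**Working it through.** **1. The plan's own figures.** Inputs from Protocol Section 10.2: Beta(0.5, 1.5) prior, a look after each subject from the fifth, at most 15 subjects, stop when P(DLT rate > 25%) ≥ 80%. The smallest x with 1 − BetaCDF(0.25; 0.5 + x, 1.5 + n − x) ≥ 0.80 is 3 for n = 5-6, 4 for 7-10, 5 for 11-13 and 6 for 14. This matches Table 10. Exact binomial recursion on these boundaries gives stopping probabilities of 17.4, 30.3, 44.9, 72.4, 90.2 and 97.8% at true rates of 20, 25, 30, 40, 50 and 60%. This matches Table 11. The tables are correct for fully observed subjects; the problem lies in the definitions.

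**2. When each test is met.** The protocol test is 0.85 × 8 = 6.8, so 7 doses (6/8 = 75% fails, 7/8 = 87.5% passes). Table 6 puts the run-in doses on days 1, 3, 5, 8 and 10 and the first MTD dose on day 12.

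| Interval | Dose 7 | Dose 8 | SAP, 5 calendar days | SAP, 5 dosing days | Last dose | Last dose + 30 |
|---|---|---|---|---|---|---|
| q48h | day 14 | day 16 | day 16 | day 20 | day 42 | day 72 |
| q72h | day 15 | day 18 | day 16 | day 24 | day 42 | day 72 |
| q96h | day 16 | day 20 | day 16 | day 28 | day 40 | day 70 |
| q7d | day 19 | day 26 | day 16 | day 40 | day 40 | day 70 |

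**3. Where the tests disagree.**
- q7d, leaves on day 17: 5 run-in + 1 MTD = 6 of 8 doses. Replaceable under the protocol; evaluable under the SAP if calendar days are meant.
- q7d, 8 of 8 doses by day 26: not replaceable under Section 3.4.2. If dosing days are meant, not evaluable under the SAP until day 40.
- q48h, leaves on day 14 or 15 after 7 doses: passes the protocol test but not the SAP test on either reading.

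**4. Illustration of size.** Assumptions that are not in the documents: a share f leaves right after dose 8 (day t), the DLT hazard is constant over the window (length T), and leavers without a DLT count as DLT-free. The observed rate is (1 − f)p + f[1 − (1 − p)^(t/T)]. With p = 0.30 and base stopping probability 45%:

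| f | Observation of leavers ends | Observed rate (q48h to q7d) | P(stop early) |
|---|---|---|---|
| 10% | at dose 8 | 27.8-28.2% | 38-40% |
| 20% | at dose 8 | 25.5-26.5% | 32-35% |
| 10% | 30 days after dose 8 | 29.0-29.5% | 42-43% |
| 20% | 30 days after dose 8 | 28.1-29.0% | 39-42% |

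Example, f = 0.2, q48h, t/T = 16/72: 1 − 0.7^(16/72) = 0.076, and 0.8 × 0.30 + 0.2 × 0.076 = 0.255. With 30 more days, t/T = 46/72: 1 − 0.7^(46/72) = 0.204, and 0.24 + 0.2 × 0.204 = 0.281.

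**5. The opposite error.** If DLT-free leavers are dropped but leavers with a DLT are kept, the rate is observed/(observed + (1 − f)(1 − p)). With f = 0.2 and observation ending at dose 8, this is 0.255/(0.255 + 0.56) = 0.313 on q48h and 0.265/(0.265 + 0.56) = 0.321 on q7d. A true 30% reads as 31-32%, and stopping rises to 49-51%.

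**The case against.** The wording mismatch is hard to dispute, but the case against a material bias is substantial.

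- **Stopping drug does not end observation.** A safety visit is due 30 (+7) days after the last dose, including for those who withdraw (Section 7.2.4, Table 5 footnote b). Adverse events are collected for at least 30 days after the last dose (Section 9.2.2.1). This stands for most leavers. Gaps remain for consent withdrawal and study discontinuation (visit done immediately), new anti-tumor therapy (visit brought forward) and loss to follow-up. No evaluability rule requires the visit.
- **The window may be shorter for a leaver.** Section 6.2.1.2.2 ties it to the last SC dose, so a subject who stops on day 16 can be read as having a window to day 46. That is arguable, and it is a reason to state the end point.
- **Toxicity leavers are already counted.** Treatment-related toxicity leading to removal from study is a DLT at any grade (Section 6.2.1.2.3). This stands.
- **Progression is not a listed exit in Period 2.** Sections 6.2.1.4.3 and 8.3.1 limit it to Period 1. This stands.
- **The link to Table 10 is not explicit.** The boundary runs from the fifth subject treated and is not tied to the DLT set. DLT summaries are specified for Period 1 only (Protocol 10.4.1, SAP 10.5.1.1). The DLRT also reviews all adverse events in the window. This stands, and it leaves the boundary's denominator unstated.
- **Section 3.4.2 is permissive.** It says such subjects may be replaced, and the Section 3.4 lead-in separately allows replacement of non-evaluable subjects. It acts as a definition only because Section 6.2.1.2.2 has none for Period 2.

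**Conclusion.** The inconsistency holds and needs no modelling. The protocol gives no Period 2 evaluability definition at the place it points to. Its replacement rule and the SAP rule classify the same Table 6 subject differently on either reading of 5 days. Neither requires a DLT-free subject to be observed to the end of the window. The SAP does not declare the difference.

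A reader might infer three stronger claims that the documents do not support.

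- **That the chance of stopping falls from 45% to 32-35%.** This needs 20% of subjects to leave at dose 8 and vanish, under constant hazard. The 20% in Section 3.3 concerns Period 1 run-in leavers and Period 2 subjects who leave before sufficient SC dosing, and those are replaced. No rate of leaving after dose 8 is given. A fair range for 10-20% leaving is 39-43% with 30-day follow-up and 32-40% without it. Early-loaded toxicity would make the loss smaller.
- **That both rules keep every subject who leaves in weeks 3-4.** On q7d this is true of the SAP rule only if calendar days are meant. With dosing days it is not met until day 40.
- **That such leavers cannot be replaced.** The text does not settle this.

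**What to change.** Write one Period 2 definition and use it in Protocol Sections 6.2.1.2.2 and 3.4.2 and SAP Sections 6, 7.3 and 8.1.1.2. A subject is evaluable with a DLT in the window, or with at least 7 of the first 8 planned doses and observation to the end of the window. State whether that end is counted from the last dose actually given.

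Delete the SAP's 5-day criterion. Reconcile the SAP's Cycle 2 bullet as well: it refers to 112 µg/day cIV for 42 days, while the SAP's own Optional Cycle 2 entry describes a stepped cIV schedule and also allows SC dosing.

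State that Table 10 is applied to this set. Report the boundary count and the Period 2 DLT rate both with and without DLT-free early leavers, because excluding only them biases the rate upward (step 5 of the working).

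Cost: amendment and SAP wording, and a few replacements (at 10-20% leaving, 15 × 0.10 to 15 × 0.20, or about 1.5 to 3 subjects). A DLT-free subject who completes dosing would not be confirmed evaluable until about day 70, which is awkward with a look after every subject. The text should say how subjects still in their window are handled at each look.

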### 3.5 Estimated Study Duration

#### 3.5.1 Study Duration for Subjects

For an individual subject, the length of participation includes a 14 day screening period, up to a 14 week treatment period (6 weeks for cycle 1 in Period 1 and Period 2 and 6 weeks for the optional Cycle 2, separated by a 14 day treatment free interval), and a safety follow-up visit (30 days [+ 7 days] after the last dose of study treatment).

For subjects who complete the protocol from the date of first dose through optional Cycle 2, the entire duration of the study will take approximately 20 weeks to complete. However, individuals' study duration will vary depending on administration of an optional second cycle and tolerability of blinatumomab by an individual subject.

#### 3.5.2 End of Study

End of Trial: the time when the last subject is assessed or receives an intervention for evaluation in the study; the final analysis will occur at this time.

## 4. SUBJECT ELIGIBILITY

Before any study-specific activities/procedure, the appropriate written informed consent must be obtained (see [Section 11.1](#)).

Investigators will be expected to maintain a screening log of all potential study candidates that includes limited information about the potential candidate (eg, date of screening).

### 4.1 Inclusion and Exclusion Criteria

#### 4.1.1 Inclusion Criteria

101. Subject has provided informed consent
102. Age  $\geq$  18 years old at the time of informed consent
103. Subjects must have a histologically determined B cell NHL subtype as defined in the bullets below. In addition, they must have disease that is primary refractory after initial therapy or have relapsed disease.
  - Follicular Lymphoma I, II, IIIA
  - Marginal zone lymphoma (extranodal, nodal, or splenic). Subjects with gastric mucosa-associated lymphoid tissue must have progressed after *Helicobacter pylori* therapy and radiation. Subjects with splenic marginal zone lymphoma must have prior splenectomy.
  - Lymphoplasmocytic lymphoma
  - Mantle cell lymphoma ([MCL] with the exception of aggressive MCL, defined as Ki67 > 30%, or blastoid histology)
  - Small lymphocytic lymphoma

104. Subjects without standard therapy alternatives, or contraindicated for standard therapy by investigator, or subjects unwilling to receive standard therapy. The disease status must be 1 of the following:
  - primary refractory (at least 1 prior line of therapy)
  - relapsed within 1 year of first response
  - responded to initial therapy for  $\geq 1$  year and relapsed after 2 or more lines of therapy, including an anti-CD20 monoclonal antibody
105. Measurable disease that has not been previously irradiated on positron emission tomography–computed tomography (PET-CT), or computed tomography (CT), of at least 1.5 cm within the last 21 days before the start of IP treatment.
106. Eastern Cooperative Oncology Group (ECOG) performance status  $\leq 2$  ([Appendix C](#)).
107. Life expectancy  $\geq 3$  months as determined by the treating physician.
108. Subjects must have adequate organ and bone marrow function at screening as defined below:
  - Hematological:
    - peripheral neutrophils  $> 500/\mu\text{L}$  prior to start of treatment
    - hemoglobin  $\geq 8$  g/dL
    - platelets  $\geq 50,000/\mu\text{L}$
  - Hepatic:
    - aspartate aminotransferase (AST)/Alanine aminotransferase (ALT)  $< 5 \times$  upper limit of normal (ULN)
    - total bilirubin  $\leq 1.5 \times$  ULN
  - Renal:
    - creatinine clearance  $\geq 50$  mL/min (Cockcroft-Gault)

#### 4.1.2 Exclusion Criteria

201. Currently receiving treatment in another investigational device or drug study, or less than 30 days between ending treatment on another investigational device or drug study(ies) and start of IP treatment. Other investigational procedures while participating in this study are excluded.
202. Known hypersensitivity to immunoglobulins or any other component of the study drug.
203. Subject likely to not be available to complete all protocol required study visits or procedures to the best of the subject and investigator's knowledge.
204. History or evidence of any other clinically significant disorder, condition or disease (with the exception of those outlined above) that, in the opinion of the investigator or Amgen physician, if consulted, would pose a risk to subject safety or interfere with the study evaluation, procedures or completion.
205. Subjects who have had treatments with anti-cancer agents including rituximab or obinutuzumab and/or other monoclonal antibody or radioimmunotherapy within 6 weeks prior to starting IP treatment.

206. Autologous stem cell transplantation within 12 weeks prior to starting IP treatment or past history of allogeneic stem cell transplantation.
207. Subjects who have received anti-CD 19 targeted therapies, chimeric antigen receptor T-cell or other cellular therapies for the treatment of their lymphoma.
208. Subjects with suspected or known brain metastases should be excluded from this clinical study because of their poor prognosis and because they often develop progressive neurologic dysfunction that would confound the evaluation of neurologic and other adverse events.
209. Infection with human immunodeficiency virus (HIV) or chronic infection with hepatitis B virus or hepatitis C virus.
210. History of or clinically relevant central nervous system (CNS) pathology such as epilepsy, recurrent seizures, paresis, aphasia, apoplexia, severe brain injuries, cerebellar disease, organic brain syndrome, or psychosis.
211. History of malignancy other than their lymphoma with the exception of:
  - Malignancy treated with curative intent and with no known active disease present for  $\geq 3$  years before enrollment and felt to be at low risk for recurrence by the treating physician
  - Adequately treated non-melanoma skin cancer or lentigo maligna without evidence of disease
  - Adequately treated cervical carcinoma in situ without evidence of disease
  - Adequately treated breast ductal carcinoma in situ without evidence of disease
  - Prostatic intraepithelial neoplasia without evidence of prostate cancer
  - Adequately treated urothelial papillary noninvasive carcinoma or carcinoma in situ.
212. Uncontrolled intercurrent illness including, but not limited to, ongoing or uncontrolled systemic fungal, bacterial, viral, or other infection, symptomatic congestive heart failure, unstable angina pectoris, cardiac arrhythmia, or psychiatric illness/social situations that would limit compliance with study requirements.
213. A female who is pregnant or breastfeeding or planning to become pregnant or breastfeed during treatment and for an additional 48 hours (Period 1) or **96** hours (Period 2), respectively, after the last dose of blinatumomab (Female subjects of childbearing potential should only be included in the study after a confirmed menstrual period and a negative highly sensitive urine or serum pregnancy test).
214. A female of childbearing potential unwilling to use a highly effective method of contraception during treatment and for an additional 48 hours (Period 1) or **96** hours (Period 2), respectively, after the last dose of blinatumomab. Refer to [Section 6.9](#) for additional contraceptive requirement information.

